#### 5.10.4.6.2 PV responsibilities

PV will follow their own Standard Operating Procedures and a study specific Safety Management to ensure that case processing of events occurs within appropriate regulatory timeframes. PV will submit Development Safety Update Reports (DSURs) to competent authorities.

#### 5.10.4.6.3 Reporting SUSARs in International Studies

The mechanism for reporting SUSARs that occur outside of the UK to the MHRA, and those that occur outside of the US to the FDA will be covered in the trial specific safety management plan.

## 5.10.4.6.4 Annual Progress Reports

An annual progress report (APR) will be submitted by the sponsor to the UK REC within 30 days of the anniversary date on which the favourable opinion was given, and annually until the trial is declared ended. Annual IRB applications for continuing review will be submitted with sufficient time to allow review and approval of trial continuation.

#### **5.10.5 Quality Assurance and Control**

#### 5.10.5.1 Risk Assessment

The Quality Assurance (QA) and Quality Control (QC) considerations for this study are based on the MeiraGTx UK II Ltd. Quality Management strategy that includes a formal Risk Assessment, and that

acknowledges the risks associated with the conduct of the study and proposals of how to mitigate them through appropriate QA and QC processes. Risks are defined in terms of their impact on: the rights and safety of participants; project concept including trial design, reliability of results and institutional risk; project management; and other considerations.

#### 5.10.5.2 Clinical Monitoring

The frequency, type and intensity of routine and triggered on-site monitoring will be detailed in the Long-Term Follow-Up Gene Therapy Study for Achromatopsia owning to defects in CNGB3 and CNGA3 Monitoring Plan (MP) respectively. The MP will also detail the procedures for review and sign-off of monitoring reports. In the event of a request for a trial site inspection by any regulatory authority MeiraGTx UK II Ltd. must be notified as soon as possible.

#### 5.10.5.2.1 Direct access to participant records

Participating investigators must agree to allow trial related monitoring, including audits, REC review and regulatory inspections, by providing access to source data and other study related documentation as required. Participant consent for this will be obtained as part of the informed consent process for the study.

#### 5.10.5.3 Study Oversight

Study oversight is intended to preserve the integrity of the study by independently verifying a variety of processes and prompting corrective action where necessary. The processes reviewed relate to participant enrolment, consent and eligibility; adherence to policies to protect participants, including reporting of harms; completeness, accuracy and timeliness of data collection; and will verify adherence to applicable policies detailed in the Compliance section of the protocol.

In multi-centre studies oversight is considered and described both overall and for each recruiting centre by exploring the study dataset or performing site visits as described in the study Monitoring Plan.

#### 5.10.5.3.1 Clinical Management Team

A Clinical Management Team (CMT) will be set up to assist with developing the design, co-ordination and strategic management of the trial. The membership, frequency of meetings, activity (including study conduct and data review) and authority will be covered in a CMT terms of reference.

#### 6 Ethics and Dissemination

# 6.1 Research Ethics Approval

Before initiation of the study at any clinical site, the protocol, all informed consent forms and any material to be given to the prospective participant will be submitted to the Health Research Authority (HRA) for approval. Any subsequent amendments to these documents will be submitted for further approval.

The rights of the participant to refuse to participate in the trial without giving a reason must be respected. After the participant has entered the study, the clinician remains free to give alternative treatment to that specified in the protocol, at any stage, if the clinician feels it to be in the best interest of the participant. The reasons for doing so must be recorded. The participant remains free to change their mind at any time about the protocol follow-up without giving a reason and without prejudicing their further treatment.

# 6.2 Regulatory Authority Approvals

This protocol will be submitted to the national competent or equivalent authority (i.e. MHRA in the UK and FDA in the USA).

This study does not involve the administration of an ATIMP. However, as the intention is to collect safety and efficacy data on participants administered an Advanced Therapy Investigational Medicinal Product in a previous trial (CNGB3 or CNGA3), which involves the application of monitoring procedures that are outside of the course of current practice for the management of achromatopsia, a CTA approval is required in the UK and an Investigational New Drug (IND) Application approval is required in the United States.

The progress of the study, safety issues and reports, including expedited reporting of SUSARs, will be reported by the sponsor or authorised delegate to the Competent Authority, regulatory agency or equivalent in accordance with relevant national and local requirements and practices.

# 6.3 Other Approvals

A copy of the confirmation of local capacity and capability review (or other relevant approval as above) and of the Participant Information Sheet (PIS) and consent form on local headed paper must be forwarded to MeiraGTx UK II Ltd. as part of the site initiation process prior to the site being designated 'open to recruitment' status.

Participating sites receiving funding or support from the US government will obtain a Federal Wide Assurance (FWA).

#### 6.4 Protocol Amendments

MeiraGTx UK II Ltd. will be responsible for amendments to the protocol. MeiraGTx UK II Ltd. will be responsible for ensuring that protocol amendments are submitted to national competent authorities, and to investigators at each study site.

Investigators at each clinical site will be responsible for submitting protocol amendments to the relevant REC/IRBs for approval, as well as any additional competent authorities in each country that require notification (e.g. the NIH OBA).

#### 6.5 Consent or Assent

Potential participants will be provided with a Participant Information Sheet (PIS) and consent form, and given time to read it fully. Following a discussion with a medically qualified investigator or suitable trained and authorised delegate, any questions will be satisfactorily answered and if the participant is willing to participate, written informed consent will be obtained. During the consent process it will be made completely and unambiguously clear that the participant (or parent or guardian of a child) is free to refuse to participate in all or any aspect of the study, at any time and for any reason, without incurring any penalty or affecting their treatment (or that of their child).

Minors (as defined by local law) who are unable to consent for themselves will not be enrolled in the study without the consent of their parent(s) or legal guardian(s). Children or adolescents will be asked to assent or agree. A Participant Information and Assent sheet that describes the details of the study, study procedures, and risks in simplified form will be provided to minors who have the capacity to provide informed assent. Participation will be refused in the event that assent is not given. Assent forms do not substitute for the consent form signed by the participant's legally authorized representative. If a child becomes an adult during their participation in the trial, then he/she will be reconsented as an adult at the time of their next scheduled visit.

Consent will be re-sought if new information becomes available that affects the participant's consent in any way. This will be documented in a revision to the participant information sheet and the participant will be asked to sign an updated consent form. These will be approved by the appropriate ethics committee prior to their use. Consent will also be re-sought in the event that a child's carer changes.

A copy of the approved consent form is available from MeiraGTx UK II Ltd. study team.

# 6.6 Confidentiality

All data will be handled in accordance with the UK General Data Protection Regulation 2018 (GPDR), the Health Insurance Portability and Accountability Act of 1996 (HIPAA) or appropriate local data protection requirements.

These regulations require a signed subject authorization informing the participants of the following:

- What protected health information (PHI) will be collected from participants in this trial
- Who will have access to that information and why
- Who will use or disclose that information
- The rights of a research participant to revoke their authorization for use of their PHI.

In the event that a participant revokes authorization to collect or use PHI, the investigator, by regulation, retains the ability to use all information collected prior to the revocation of subject authorization. For participants that have revoked authorization to collect or use PHI, attempts should be made to obtain permission to collect at least vital status (i.e., that the subject is alive) at the end of their scheduled trial period.

Participant confidentiality will be held strictly in trust by the investigators, study staff, and the sponsor and their agents, to the extent provided by Federal, state, and local law. This confidentiality is extended to cover testing of biological samples and genetic tests in addition to any trial information

relating to participants. All laboratory specimens, evaluation forms, reports, and other records that leave the site will be identified only by a coded number to maintain subject confidentiality. All records will be kept locked and all computer entry and networking programs will use coded numbers only. Participants will not be identified in any publicly released reports of this trial.

Access to study records will be limited to the minimum number of individuals necessary for quality control, audit and analysis. Clinical information will not be released without written permission of the participant, except as necessary for study-related monitoring, audits, REC/IRB review, and regulatory inspections by University or government entities. In these cases, the clinical site will provide direct access to all source data, documents, and records maintained by the investigator, including but not limited to, medical records (office, clinic, or hospital) for the study participants. Study participants will be informed of this during the informed consent process.

No information concerning the study or the data will be released to any unauthorized third party without prior written approval of MeiraGTx UK II Ltd.

The Case Report Forms (CRFs) will not bear the participant's name or other personal identifiable data. The participant's initials, date of birth and study identification number, will be used for identification.

#### 6.7 Declaration of Interests

This study is funded by MeiraGTx UK II Ltd.

declares ownership of minority shareholdings in MeiraGTx UK II Ltd. and receipt of payment for consultancy services.

declares ownership of minority shareholdings in MeiraGTx UK II Ltd. and receipt of payment from MeiraGTx UK II Ltd. for consultancy services.

# 6.8 Indemnity

MeiraGTx UK II Ltd. holds insurance to cover participants for injury caused by their participation in the clinical study. Participants may be able to claim compensation if they can prove that MeiraGTx UK II Ltd. has been negligent. However, as this clinical study is being carried out in a hospital, the hospital continues to have a duty of care to the participant in the study. MeiraGTx UK II Ltd. does not accept liability for any breach in the hospital's duty of care, or any negligence on the part of hospital employees. This applies whether the hospital is an NHS Trust or not. This does not affect the participant's right to seek compensation via the non-negligence route.

Participants may also be able to claim compensation for injury caused by participation in this clinical trial without the need to prove negligence on the part of MeiraGTx UK II Ltd. or another party. Participants who sustain injury and wish to make a claim for compensation should do so in writing in the first instance to the Chief Investigator, who will pass the claim to MeiraGTx UK II Ltd's insurers.

Hospitals selected to participate in this clinical trial shall provide clinical negligence insurance cover for harm caused by their employees and a copy of the relevant insurance policy or summary shall be provided to MeiraGTx UK II Ltd, upon request.

#### 6.9 Finance

This follow up study is fully funded by MeiraGTx UK II Ltd. It is not expected that any further external funding will be sought.

#### 6.10 Archiving

Study documents should be retained for a minimum of 2 years after an FDA marketing application is approved and until there are no pending or contemplated marketing applications, or if an application is not approved, until 2 years after shipment and delivery of the drug for investigational use has been discontinued and FDA is notified. For gene therapy trials, current Federal and State of Michigan requirements state that research records should be kept indefinitely, until further notice. Archiving of REC/IRB notices should be maintained according to local and/or institutional requirements.

Essential documents are those which enable both the conduct of the study and the quality of the data produced to be evaluated and show whether the site complied with the principles of Good Clinical Practice and all applicable regulatory requirements.

MeiraGTx UK II Ltd. will notify sites when trial documentation can be archived and which documents must be archived for the longer 30-year period. All archived documents must continue to be available for inspection by appropriate authorities upon request.

Destruction of essential documents will require authorisation from the Sponsor.

#### 6.11 Access to Data

The investigators/ institutions will permit study-related monitoring, audits, REC review, and regulatory inspections, providing direct access to source data/documents. Study participants are informed of this during the informed consent discussion. Participants will consent to provide access to their medical notes.

Requests for access to study data will be considered, and approved in writing where appropriate, after formal application to MeiraGTx UK II Ltd.

#### 6.12 Ancillary and Post-study Care

At the end of the follow up study, participants will resume usual standard of care within their primary care teams.

## **6.13 Publication Policy**

All proposed scientific publications will be discussed with the Sponsor prior to publication. Study progress reports and significant findings may be presented at scientific forums/meetings and/or published during the course of the study. The results of the study will be disseminated regardless of the direction of effect.

# 7. Ancillary Studies

There are no currently planned ancillary studies. Any future ancillary studies will be subject to separate funding and will be submitted for ethical and regulatory review as appropriate.

# **8** Protocol Amendments

Protocol Version and Date	Reason for Amendment
Protocol v1.0 dated 10 February 2017	Initial version
Protocol v2.0 dated 05 June 2019	Addition of Full Field Stimulus Testing at all visits in line with interventional protocol.  Reduction in assessment burden in line with interventional protocols
	Addition of CNGA3 Achromatopsia trial
Protocol v3.0 dated 26 June 2019	Administrative error
Protocol v4.0 dated 07 Sep 2020	Assessment and Management of risks updated  Evaluation of immune responses section added and Serology tests (AAV8 antibody and transgere antibody testing) added to assessments in protocol text and in assessments schedule.  Independent Data Monitoring Committee and Safety Data Monitoring Committee information updated  Administrative errors corrected
Protocol v5.0 dated 02Dec2021	Update to include patients and data from the MGT012 trial.  Addition of Light-sensitivity testing/Photoaversion testing, Contrast sensitivity, Static perimetry and Quality of Life assessments to be performed in all participants  New wording to the expectedness of AE/SAE.
Protocol v6.0 dated 03Dec2021	Administrative error

	3.5.8	Photoaversion (PA)	Error! Bookmark not defined.
	3.5.9	Quality of Life	16
	3.5.10	Multiplicity	18
4	CHANG	GES FROM PROTOCOL-SPECIFIED ANALYSIS	18
5	Progran	nming Specifications	18
App	endix A:	References	19

LIST OF ABBREVIATIONS

Abbreviation	Definition
AE	Adverse event
AO	Adaptive optics
ATIMP	Advanced therapy investigational medicinal product
BCEA	Bivariate contour ellipse area
BMI	Body mass index
CF	Counting fingers
CI	Confidence interval
CMT	Clinical Management Team
CSF	Contrast Sensitivity Function
CTCAE	Common Terminology Criteria for Adverse Events
DA	Dark adapted
ELISA	Enzyme-linked Immunosorbent Assay
ERG	Electroretinography
ETDRS	Early Treatment Diabetic Retinopathy Study
FAF	Fundus Autofluorescence
FAS	Full Analysis Set
FST	Full-field Stimulus Testing
НМ	Hand motion
IDMC	Independent Data Monitoring Committee
ISCEV	International Society for Clinical Electrophysiology of Vision
IVI	Impact of visual impairment
KG	Kilograms
LP	Light perception
MedDRA	Medical Dictionary for Regulatory Activities
mfERG	Multifocal electroretinography
mL	Millilitre
NLP	No light perception
PCR	Polymerase chain reaction
PERG	Pattern electroretinography

Abbreviation	Definition
PT	Preferred term
RPGR	Retinitis Pigmentosa GTPase Regulator
SAE	Serious adverse event
SAF	Safety analysis set
SAP	Statistical analysis plan
SD	Standard deviation
SD-OCT	Spectral domain optical coherence tomography
SOC	System organ class
SUN	Standardisation of uveitis nomenclature
TEAE	Treatment emergent adverse event
UK	United Kingdom
US	United States
VAS	Visual analogue scale
VG	Vector genome
WHO	World Health Organization

1 INTRODUCTION

The purpose of this Statistical Analysis Plan (SAP) is to provide a description of the statistical methods to be implemented for the analysis of data from the study with protocol number MGT007. The SAP will be finalized prior to database lock. Any deviations from the SAP after database lock will be documented in the final Clinical Study Report (CSR).

2 STUDY OVERVIEW

2.1 Study Objectives

2.1.1 Primary Objective

The primary research objective is to assess the longer-term safety of AAV8-hCARp.hCNGB3 for CNGB3 gene replacement and AAV8-hG1.7p.coCNGA3 for CNGA3 gene replacement in the retina administered to participants in the CNGB3 and CNGA3 trials, measured by the presence or absence of adverse events, the assessment of visual acuity, and loss of light perception.

2.1.2 Secondary Objective

The secondary research objective is to explore the longer-term efficacy of AAV8-hCARp.hCNGB3 and AAV8-hG1.7p.coCNGA3 in improving visual and retinal function, and quality of life.

2.2 Study Design

2.2.1 Overview

Participants will be invited to provide consent for this longer-term follow-up study during the CNGB3 (MGT006) trial or CNGA3 (MGT012) trial. During this longer-term follow-up study participants will be assessed for safety for up to 60 months following AAV8-hCARp.hCNGB3 or AAV8-hG1.7p.coCNGA3 administration in study MGT006 or study MGT012.

The duration of long-term follow-up is therefore consistent with the recommendations of the current CHMP Guideline on Follow-up of Patients Administered with Gene Therapy Medicinal Products (EMEA/CHMP/GTWP/60436/2007) of 22 October 2009, where it is stated that, for viral vectors without integration, latency or reactivation potential, a brief clinical history and sample testing should be performed pre-treatment, at 3, 6 and 12 months after treatment, and then yearly thereafter for a minimum of 5 years (and, if non-clinical tests or evidence from other clinical trials using identical vectors or modifications of vectors indicate a potential for integration or late re-activation, the monitoring should be extended to continue yearly after those 5 years until data indicate that there is no longer any risk to be followed). Further, although the Food and Drug Administration (FDA) Guidance for Industry: Gene Therapy Clinical Trials – Observing Subjects for Delayed Adverse Events (November 2006) recommends a standard 15-year period of follow-up, it is also noted that a shorter period of follow-up may be possible if the vector does not integrate and has no potential for latency and reactivation. The follow-up study will be a non-intervention study designed to collect data on longer-term safety and efficacy at the equivalent of 9, 12, 18, 24, 36, 48, and 60 months following ATIMP administration.

2.2.2 Randomization and Blinding

The study is an open-label non-randomized study.

2.2.3 Sample Size Determination

This is a long-term follow-up study; therefore, there is no formal sample size calculation.

23 and 11 participants were randomized and dosed in the MGT006 and MGT012 studies, respectively. All participants enrolled in the MGT006 and MGT012 studies were invited to participate in this follow-up study.

2.3 Study Endpoints

2.3.1 Primary Endpoint

The primary endpoint is to assess the longer-term safety of AAV8-hCARp.hCNGB3 for *CNGB3* gene replacement and AAV8-hG1.7p.coCNGA3 for *CNGA3* gene replacement in the retina administered to participants in the MGT006 and MGT012 studies, measured by the occurrence of any adverse events that are related to the study drug and loss of light perception as measured by a deterioration in visual acuity by 15 or more early treatment diabetic retinopathy study (ETDRS) letters.

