3.1.4 Summary Statistics

Categorical data will generally be summarized with counts and percentages of subjects. The denominator used for the percentage calculation will be clearly defined. Continuous data will generally be summarized with descriptive statistics including n (number of non-missing values), mean, median, standard deviation, Q1, Q3, minimum, and maximum.

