3.4 Safety Evaluation

3.4.1 Adverse Events

AE will be coded using the latest MedDRA dictionary version. The version used will be indicated in the data summaries and listings.

A TEAE is defined as an AE that started on or after the start of the administration of ATIMP. If adverse event dates are incomplete and it is not clear whether the adverse event was treatment-emergent, it will be assumed to be treatment-emergent.

A treatment-related TEAE is defined as a TEAE that is possibly, probably, or definitely related to ATIMP or ATIMP surgery. If the TEAE has a missing relationship it is assumed to be related to ATIMP for analysis purposes.

A summary table will present the following by dose group in the dose escalation and dose expansion phase:

- TEAEs (events and participants).
- Serious TEAEs (events and participants).
- Serious study treatment-related TEAEs (events and participants).
- TEAEs by severity (CTCAE grade version 4.0) (events and participants).
- TEAEs by relationship to ATIMP and the pooled ATIMP-related [possibly, probably, and related] category (events and participants).
- TEAEs by relationship to ATIMP surgery and the pooled ATIMP-related [possibly, probably, and related] category (events and participants).
- TEAEs leading to withdrawal from study (participants only).
- TEAEs leading to death (participants only).

If a participant experienced more than one TEAE, the participant will be counted once using the most related event for the "by relationship to study treatment" and "related to study treatment" summaries and at the worst severity for the "by severity" summary.

The following tables will be presented:

- TEAEs by SOC and PT.
- TEAEs by SOC, PT, and severity (CTCAE grade version 4.0).
- TEAEs by SOC, PT, and relationship to ATIMP and the pooled related categories (related [possibly, probably, and related]).
- TEAEs by SOC, PT, and relationship to ATIMP surgery and the pooled related categories (related [possibly, probably, and related]).

For all of the above, SOC and PT will be presented in decreasing frequency of the total number of participants with TEAEs.

Further details of the above five tables are given below:

- If a participant experienced more than one TEAE the participant will be counted once for each SOC and once for each PT
- If a participant experienced more than one TEAE the participant will be counted once for each PT.

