3.5.2 Visual Acuity

Visual acuity was assessed at the Month 9, 12, 18, 24, 36, 48, and 60 visits.

4 meter refraction of the sphere, cylinder, and axis of each eye will be measured. Best-corrected ETDRS visual acuity will be measured.

The arithmetic mean of the multiple observations at baseline will be used as the baseline value.

Achievement of visual improvement above the test-retest variation (yes/no) as measured by a number of ETDRS letters will be summarized for study eye and the difference between eyes (study eye minus fellow eye) for all participants.

The 4-meter refraction (sphere, cylinder, and axis) observed values will be summarized for the study eye for all participants.

Summary statistics of all ETDRS visual acuity observed values and the change from baseline by study eye and the difference between eyes (study eye minus fellow eye) for all participants will be presented.

The difference between the study eye and the fellow eye of ETDRS letters, the difference at each visit, along with its change from baseline data, will be summarized. At each post-baseline visit, the change from baseline in the difference between the study eye and the fellow eye will be tested by a nonparametric Wilcoxon signed rank test as the primary method. The p-value from the t-test and the Shapiro-Wilk Normality test will also be provided.

All visual acuity data will be listed.

In-text displays:

- Average Plot of BCVA (ETDRS Letters) Change from Baseline Over Time
- Individual Plot of BCVA (ETDRS Letters) Change from Baseline Over Time

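### SAP 2.3.1 measures loss of light perception by a 15-letter acuity loss, merging two safety measures that the objective keeps apart, and the SAP names no table for either

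*SAP*

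**What the plan says.** The objective, in the same words in protocol 4.5.1 and SAP 2.1.1, is longer-term safety "measured by the presence or absence of adverse events, the assessment of visual acuity, and loss of light perception". That is three measures. Protocol 5.5.1 gives the primary outcome simply as long-term safety and sets no letter threshold.

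SAP 2.3.1 then defines the visual part of the primary endpoint as "loss of light perception as measured by a deterioration in visual acuity by 15 or more early treatment diabetic retinopathy study (ETDRS) letters".

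Acuity is analysed only under efficacy, in SAP 3.5.2. The one categorical summary there is this: "Achievement of visual improvement above the test-retest variation (yes/no) as measured by a number of ETDRS letters will be summarized for study eye", with the same for the between-eye difference. The continuous output is "Summary statistics of all ETDRS visual acuity observed values and the change from baseline by study eye and the difference between eyes", and SAP 3.1.4 gives the statistics, which include "median, standard deviation, Q1, Q3, minimum, and maximum". SAP 3.5.2 also plans an individual plot of change in acuity and a full listing.

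**The concern.** This is the primary endpoint of a safety study, and its visual part does not measure the event that it names. A loss of 15 letters is a change on a chart that the eye may still be reading. Loss of light perception is a much more severe state, reported off the chart. If the first is published under the name of the second, a reader will think that eyes went blind when they lost three lines of letters. If no eye meets the rule, a reader may take that as a statement about light perception, which the rule never examined.

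The rule is also incomplete. It does not say which eye counts or at which visit the loss must occur. Nor does it name the reference value, although SAP 3.1.1 and 3.5.2 supply a baseline. With no table named, the report need not give n/N for this part of its own primary endpoint.

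**Working it through.** The documents give no event rate, power or sample-size figure for this endpoint (SAP 2.2.3 states that there is no formal calculation), so there is no figure of the plan to reproduce. The check sets the texts side by side and adds some short arithmetic.

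**1. Objective against endpoint**

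| Measure in the objective (protocol 4.5.1, SAP 2.1.1) | Treatment in SAP 2.3.1 |
|---|---|
| Adverse events | Kept, as related events |
| Visual acuity | Used only as the yardstick for light perception |
| Loss of light perception | Named, but measured by a 15-letter loss |

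Three measures become two, and the name of the second does not match its rule. Example: baseline 50 letters, loss 15, result 50 − 15 = 35 letters. The rule is met and the eye still reads the chart.

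**2. Outputs that could carry the visual part**

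- SAP 3.4 (safety): adverse-event tables, pregnancy listing, intraocular pressure summaries, and listings for slit lamp, autofluorescence and fundus photography. Nothing on acuity or light perception.
- SAP 3.5.2 (acuity): yes/no summaries are for improvement, none for loss. Summary statistics, between-eye tests, plots and a listing follow.
- SAP 4: no entry on the endpoint wording.

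**3. Can the summary statistics stand in for a count?** Take an invented set of 34 participants (23 + 11 dosed, SAP 2.2.3) in which k lose 30 letters and the rest gain 2. Mean = [2(34 − k) − 30k]/34.

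| k | Mean | Median | Q1 | Minimum |
|---|---|---|---|---|
| 1 | (66 − 30)/34 = 1.1 | 2 | 2 | −30 |
| 2 | (64 − 60)/34 = 0.1 | 2 | 2 | −30 |
| 3 | (62 − 90)/34 = −0.8 | 2 | 2 | −30 |

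The minimum shows that a large loss occurred, but not how many. There is an exception: in a complete dose group of three, the minimum, median and maximum are the three values, so a per-visit count can be read off. That fails for the group of 12 and for the product totals. Per-visit statistics also do not link a participant across the seven visits. The individual plot and the listing do, but the counting is then left to the reader.

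**4. What one participant is worth.** The dose table in SAP 3.1.5 adds up: 3 + 12 + 3 + 5 = 23 and 3 + 3 + 5 = 11. If all dosed participants enrolled:

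- by product: 1/23 = 4.3% and 1/11 = 9.1%;
- by dose level: 1/12 = 8.3%, 1/5 = 20.0%, 1/3 = 33.3%.

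**The case against.** The best defence is that the SAP needs no further table. SAP 3.1.4 says that categorical data are generally given as counts and percentages, SAP 3.1.5 that all data are summarised by dose level with study totals, and SAP 3.2.2 that safety uses the Safety Analysis Set. A yes/no endpoint defined in 2.3.1 could fall under these defaults. SAP 5 leaves the programming detail to a separate document that is not available here. The 15-letter threshold is explicit, so analysts would apply the same cut-off. Every acuity value is listed and plotted. A clinically significant loss may be recorded as an adverse event (protocol 5.10.4.5) and then counted under its coded term in the tables of SAP 3.4.1. The analysis is descriptive (protocol 5.9.3).

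Much of this stands, and it limits the consequence. It does not remove the defect. The defaults say how a variable is summarised, not that this one will be, and SAP 3.5.2 spells out improvement while leaving loss unmentioned. An explicit threshold under the wrong name is still the wrong name. The adverse-event route depends on a judgement of clinical significance and does not apply the 15-letter criterion.

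It is also fair to say that SAP 4 covers changes from the protocol's analysis, and the protocol's outcome and statistical sections specify only safety. The mismatch is with the objective's wording, so the missing entry is a point of clarity and not a concealed change.

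**Conclusion.** The point holds as an error in the definition of the primary endpoint and a missing named count, and should be fixed before the SAP is final. The mismatch follows from the text alone. The percentage-point figures assume that all 23 and 11 dosed participants enrolled; with fewer, each participant weighs more.

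Four stronger readings are tempting and are not supported.

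- **Visual losses would go unreported.** They would not. They remain visible in the minimum, the individual plots, the listings and possibly the adverse-event tables.
- **A light-perception analysis was planned and dropped.** A reader might infer this from the SAP abbreviation list, which contains the entry "No light perception". The same list carries RPGR, mfERG, BCEA and PCR, which later sections also do not use, so the entry may simply be carried over.
- **The endpoint discards unrelated adverse events.** SAP 2.3.1 does speak of "the occurrence of any adverse events that are related to the study drug", but SAP 3.4.1 tabulates all treatment-emergent events and defines relatedness for both product and surgery: "A treatment-related TEAE is defined as a TEAE that is possibly, probably, or definitely related to ATIMP or ATIMP surgery". This is a matter of wording only.
- **The rule miscounts a known number of eyes, through measurement noise or because poor baseline acuity leaves no room to lose 15 letters.** The documents give no acuity SD, score floor or baseline acuities, so no such number can be derived.

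**What to change.** Restate SAP 2.3.1 with two separate visual components beside the adverse-event component:

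- (a) a loss of 15 or more ETDRS letters from baseline in the study eye at any scheduled post-baseline visit (Months 9 to 60 in SAP 3.5.2);
- (b) loss of light perception, meaning that no light perception was recorded in an eye that had it at baseline.

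Add one safety table on the Safety Analysis Set with n/N (%) for (a) and (b), by product and dose level. A footnote should say that (b) can be counted only where off-chart acuity was recorded, because the protocol names ETDRS acuity in each eye but no separate light-perception test. Unscheduled values stay in the listings, as SAP 3.1.5 already provides. A further count of (a) confirmed at two consecutive visits is optional; the documents require persistence only for improvement in visual function. Add a line to SAP 4 that the endpoint wording differs from the protocol objective.

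The cost is a few lines of SAP text and one table. Component (a) uses acuity data already in the schedule. Component (b) may have few or no data, and the table should then say so. SAP 1 has the plan finalised before database lock; a later change would have to be documented in the study report.
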